3.2.2 Additional Outcomes

Beyond supporting the primary endpoint of this investigation, Spineology is evaluating additional outcome data. The investigation design allows for the assessment of objective and subjective findings. Descriptive data will be provided to characterize these additional effectiveness and safety measures:

- Mean low back VAS pain score over time through the 24-month interval
- Mean lower extremity (right and left leg) VAS scores over time through the 24-month interval
- Mean ODI score over time through the 24-month interval
- Fusion at the 12-month and the 24-month interval
- Occurrence of device-related Serious Adverse Events through the 24-month interval
- Occurrence of study-related Adverse Events through the 24-month interval
- Neurological status assessment (strength, sensation, and reflexes) over time through the 24-month interval (reporting categorized as improved, maintained, or reduced with new or increased neurological deficit being further categorized as transient (< 3 months/90 days) or longer term \geq 3 months/90 days);
- Radiographic data observed over time specific to the index level (translation, angulation, disc height, and device position)
- Subject satisfaction with procedure/outcome
- Work status over time
- Pain medication use over time
- Operative time
- Estimated blood loss
- Duration of hospitalization
- Graft site pain (as applicable)
- Adjacent segment status at 24-months post-operative assessed by quantitative and qualitative radiographic data (translation, angulation, and disc height)

3.2.3 Statistical Methods

The statistical analysis of the data obtained from this study will be performed using SAS® version 9.1 or higher. All statistical tests will be performed at the 0.05 significance level, unless otherwise indicated.

Data collected in this study will be documented using summary tables and subject data listings. Continuous variables will be summarized using descriptive statistics, specifically the mean, median, standard deviation, minimum, and maximum, and a 95% confidence interval for the mean based

on the t-distribution. Categorical variables will be summarized using frequencies and percentages and 95% exact (Clopper-Pearson) confidence intervals for the true proportions.

All analyses of effectiveness and safety will be based upon the Treated Population defined to be all treated subjects.

3.2.4 *Determination of Sample Size*

The required sample size was calculated based on the following specifications:

1. Endpoint: success rate
2. One-sided exact binomial test for a binomial proportion
3. Alpha = 0.05
4. True percentage of successes = 68%
5. Performance Goal (null percentage of successes) = 55%
6. Power = 80%

The required sample size based upon these specifications is 87 subjects. The sample size was increased to 102 subjects to take into account an assumed 15% lost to follow-up rate.

3.2.5 *Sample Size Re-Estimation*

A sample size re-estimation will be performed based on 12-month interim data.

3.2.6 *Analysis of Primary Endpoint*

The primary endpoint for this investigation is a composite endpoint of pain, function, fusion, and safety that meets all of the following criteria at the 24-month study interval:

- Pain – Improvement in low back pain score evidenced by a 20 mm reduction on a 100 mm Visual Analog Scale (VAS) when compared to baseline (Note: a lower VAS pain score indicates less pain),
- Function – Improvement in low back function evidenced by a 15 point decrease of the Oswestry Disability Index (ODI) score compared to baseline. (Note: a higher ODI score indicates greater disability with respect to low back function),
- Fusion – Bridging bone demonstrated on CT Scan
- Safety – Freedom from investigational device-related Serious Adverse Events at the index level through the 24-month study interval.

This endpoint will be summarized using the count and percentage, together with a 95% exact (Clopper-Pearson) confidence interval for the true proportion of successes. The null and alternative hypotheses for this endpoint are as follows:

$$H_0: p \leq 0.55$$

versus

$$H_1: p > 0.55$$

where p denotes the true proportion of subjects achieving success for this endpoint. The null hypothesis will be tested using a 1-sided exact binomial test for a binomial proportion conducted at the 0.05 level of significance.

Missing values for the primary endpoint at Month 24 will be imputed using the last-observation-carried-forward (LOCF) method and multiple imputation methods. For subjects who are missing at most one component of the primary endpoint at Month 24 and who have a value for the given component at Month 12, the LOCF method will be used to impute a value for that component at Month 24, so that the value of the primary endpoint at Month 24 can then be determined. Once the LOCF procedure has been performed, multiple imputation methods will be used to impute values for the remaining subjects with missing values for the primary endpoint at Month 24. The imputation procedure will be based on primary endpoint data at all previous post-baseline time points.

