2.2 INVESTIGATION OBJECTIVES

The primary objective of this investigation is to demonstrate the effectiveness of the SIFS in a lumbar interbody application. Effectiveness will be determined as a composite score that represents patient success. To be considered a patient success, each of the following criteria must be met at the 24-month study interval:

- Pain – Improvement in low back pain score evidenced by a 20 mm reduction on a 100 mm Visual Analog Scale (VAS) when compared to baseline (Note: a lower VAS pain score indicates less pain),
- Function – Improvement in low back function evidenced by a 15 point decrease of the Oswestry Disability Index (ODI) score compared to baseline. (Note: a higher ODI score indicates a greater disability with respect to low back function),
- Fusion – Bridging bone demonstrated on CT Scan
- Safety – Freedom from device-related Serious Adverse Events and secondary surgical interventions at the index level through the 24-month study interval.

In addition to the above stated primary objective, this investigation will yield data on the following outcomes, subject parameters and clinical utility:

- Variable scores over time (pain, function, fusion) as individual parameters
- Adverse Event rate(s) reported by relatedness and severity
- Neurological status over time
- Quantitative/qualitative radiographic data over time specific to the index level and contiguous levels (translation, angulation, disc height, and device position)
- Demographics
- Hospitalization Utility (duration of surgery, estimated blood loss and duration of hospitalization)
- Work status over time
- Pain medication use

Data collection is not limited to the above data points. Additional parameters will be reported on as appropriate. For a more detailed list of supplemental outcomes refer to Section 3.2 Scientific Soundness and Statistical Analysis.

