8.1 Adjudication Procedure

Each AE will be reviewed individually by a DMC/CEC. The DMC Charter is provided as **Appendix V**. Each event is initially classified as an adverse event or a non-event. A non-event is an event that does not require treatment. An event captured and determined to be a non-event will be reported as an observation. Following this determination, an adverse event is assessed for relatedness to the trial and may be classified as a study-related adverse event or a not-study-related adverse event. A not-study-related adverse event is an adverse event determined to not have a causal relationship with either the device or the procedure. All study-related adverse events are further adjudicated for severity and relatedness to the procedure/device as defined below.

Event severity refers to the degree of seriousness of the AE. The categories of event severity are: Serious Adverse Event (SAE) and a rating of mild, moderate or severe. Event relatedness refers to the association to the investigational device, fixation hardware or the surgical procedure. Event relatedness is categorized by the following associations: device related, hardware related, procedure related, other related, or unknown (undeterminable) relatedness.

For clarification, the following “relatedness” definitions will be applied in this investigation:

- **Device Related:** An adverse event that results from the presence or performance of the SIFS mesh device.
- **Hardware Related:** An adverse event that results from the presence or performance of any of the supplemental fixation device components.
- **Procedure Related:** A procedure related adverse event shall be evaluated and adjudicated in accordance with the below sub-classifications. A procedure related AE may occur as a result of one or more of the following and shall be specified as such for analysis and reporting purposes:
 - *Procedure – Device:* Occurs due to the implantation procedure for the investigational mesh device
 - *Procedure – Hardware:* Occurs due to the implantation procedure for the supplemental fixation
 - *Procedure – General Surgery:* Occurs as a result of the general surgical procedure and is not related to any of the above defined definitions or any of the below definitions.
- **Other Related:** An adverse event that occurs and is determined to have a relatedness that is not device, hardware, procedure, general surgery, or unknown relatedness.

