- **Unknown:** An adverse event that cannot be determined to have a causal relationship with either the device or procedure will be classified as unknown.

It is anticipated that resultant of the defined criteria for each relatedness determination, few adverse events will be categorized as “Other”. The severity of events will be classified by the DMC as described in the following two sections.

8.2 **Serious Adverse Event**

The DMC will first determine whether an AE is serious. A Serious Adverse Event, corresponding to FDA’s definition, is an adverse event that results in one of the following outcomes:

- requires hospitalization,
- prolongs hospitalization,
- is life-threatening,
- results in a congenital anomaly/birth defect, or
- results in death.

8.3 **Event Severity**

The DMC will adjudicate the severity of each AE. Severity is categorized as follows:

- **Severe Adverse Event:** Significant impairment of functioning; subject is unable to carry out usual activities. A severe AE requires treatment or intervention.
- **Moderate Adverse Event:** Subject experiences sufficient discomfort to interfere with or reduce their usual level of activity. A moderate AE requires treatment.

- **Mild Adverse Event:** Subject is aware of event or symptom, but event/symptom is easily tolerated. A mild AE may not require treatment.

The Clinical Event Committee shall be convened on a quarterly basis through the duration of the investigation to formally review and adjudicate study events. The DMC Chairperson shall perform an interim (continuous) review of adverse events prior to conducting the quarterly committee review(s). The Chairperson may convene a Committee meeting at his/her discretion at any time to ensure subject safety is adequately protected.

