11.0 DEFINITIONS

Adverse Event – A secondary disease or condition that develops in addition to, or at an increased rate or severity from, the expected response to treatment, necessitating further evaluation and treatment by a physician. All adverse events, whether related or unrelated to the device or procedure, shall be captured and reported. Further, all adverse events will be adjudicated by the Data Monitoring Committee and reported to FDA per protocol.

Case Report Form (CRF)/Electronic Case Report Form (eCRF)/CRF Worksheet –

- **CRF** – A document designated to record protocol required information for each subject participating in an investigation. A CRF may be provided to sites in paper copy or electronic copy. A paper CRF may be used as a worksheet providing the captured information is recorded in the electronic database.
- **eCRF** – A database equivalent electronic version of the CRF.
- **CRF Worksheet** – A paper version of a CRF used to collect data that will be entered into the eCRF. Worksheets shall be maintained in the relevant study subject's binder at the investigation site.

Centralized Monitoring – A remote evaluation carried out by sponsor personnel or representatives (e.g., clinical monitors, data management personnel, or statistician) at a location other than the site(s) at which the clinical investigation is being conducted.

Device Related – An adverse event that results from the presence, performance or implantation procedure of the investigational device (SIFS mesh).

Enrolled – For this investigation, a subject is considered enrolled after meeting all study entrance criteria, has confirmed agreement to participate in the investigation as documented through completion of the informed consent process, and has been assigned a surgical procedure date. Further, it is expected that prior to enrollment, the investigational site will have successfully negotiated the precertification process as required for pertinent insurance carriers, and obtained documentation of the carrier's precertification approval.

Extended Hospitalization – Increased duration of hospitalization based on determination of the treating investigator.

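### The safety part of the primary composite counts index-level secondary surgery as failure in Section 2.2 but not in Sections 3.2.1 and 3.2.6, so the tested endpoint is not the stated primary objective

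*Combined protocol and SAP*

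**What the plan says.** Section 2.2 presents the composite as the primary objective: "To be considered a patient success, each of the following criteria must be met at the 24-month study interval". Its safety line is "Freedom from device-related Serious Adverse Events and secondary surgical interventions at the index level through the 24-month study interval".

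Section 3.2.1 (Primary Endpoint) and Section 3.2.6 (Analysis of Primary Endpoint) repeat the pain, function and fusion lines. In both, the safety line is "Freedom from investigational device-related Serious Adverse Events at the index level through the 24-month study interval". Secondary surgery is not mentioned.

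Section 3.2.6 goes on: "The null and alternative hypotheses for this endpoint are as follows", followed by a null of at most 0.55 and a one-sided exact binomial test at 0.05. Section 3.2.4 plans for a true success rate of 68% against the 55% goal.

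Section 8.1 defines a device-related event as "An adverse event that results from the presence or performance of the SIFS mesh device". It keeps hardware-related events in a separate class: "An adverse event that results from the presence or performance of any of the supplemental fixation device components". Under Section 8.2 an event is serious if it leads to or prolongs hospitalization, is life-threatening, or results in a birth defect or death. A second operation is not in itself a criterion.

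**The concern.** The same composite has two safety definitions in current text, and they do not classify every subject alike. This is a single-arm trial judged against a fixed goal, so its conclusion depends entirely on who counts as a success. A reader of 2.2 would take the reported success rate to exclude subjects who had another operation at the treated level. The tested rate may include some of them.

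Nothing else in the plan closes the gap. The one cross-reference from 2.2 to 3.2 concerns supplemental outcomes and does not rank the definitions. The revision history lists only the original issue, so no amendment explains the difference. Secondary surgery is not among the additional outcomes in 3.2.2 or 3.2.7. Section 11 defines removal, re-operation and revision, but no analysis in 3.2 uses those terms. If the choice stays open until data are seen, the more favourable version could be picked.

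**Working it through.** **1. Who is classified differently.** Take subjects who meet the pain, function and fusion criteria at 24 months.

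| Event at the index level through 24 months | 2.2, plain reading (any secondary surgery fails) | 2.2, narrow reading (device-related surgery only) | 3.2.1 / 3.2.6 |
|---|---|---|---|
| Device-related SAE | Failure | Failure | Failure |
| Hardware revision, or other re-operation not adjudicated device-related | Failure | Success | Success |
| Device-related surgery meeting no SAE criterion | Failure | Failure | Success |
| No event | Success | Success | Success |

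Both readings of 2.2 differ from 3.2.6. The narrow reading leaves a much smaller gap, because device-related surgery that requires hospitalization is already an SAE. The edge of that gap is also not fixed: Section 11 counts the mesh implantation procedure as device related, while 8.1 files it under a procedure sub-class.

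**2. The plan's own figure.** Inputs from 3.2.4: null 0.55, alternative 0.68, one-sided alpha 0.05, power 80%, exact binomial. The smallest n that satisfies these is 87, with critical value 56:
- P(X ≥ 56 | n = 87, 0.55) = 0.0487
- P(X ≥ 56 | n = 87, 0.68) = 0.801

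This matches the stated 87. Allowing for 15% loss, 87/0.85 = 102.35; the plan states 102. The sample size is not in dispute.

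**3. Decision rule with 102 complete subjects.**
- P(X ≥ 65 | n = 102, 0.55) = 0.0464, so 65 successes pass.
- P(X ≥ 64 | n = 102, 0.55) = 0.0697, so 64 do not.
- P(X ≥ 65 | n = 102, 0.68) = 0.849.

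Expected successes at 68% are 102 × 0.68 = 69.4. From 69, it takes 69 − 64 = 5 reclassified subjects to reverse the result. From exactly 65 it takes one.

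**4. Effect of moving to the stricter definition.** Let r be the share of all subjects who succeed under 3.2.6 but fail under 2.2. The documents give no value, so r is an assumption. If 68% is the true rate under 3.2.6, the 2.2 rate is 0.68 − r, and power is P(X ≥ critical value | n, 0.68 − r):

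| r (assumed) | 2.2 rate | Power, n = 87 | Power, n = 102 |
|---|---|---|---|
| 0 | 68% | 80.1% | 84.9% |
| 1% | 67% | 74.0% | 79.2% |
| 3% | 65% | 59.7% | 64.9% |

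Every 2.2 success is also a 3.2.6 success. So the probability that the two definitions give different verdicts is the difference in power. At n = 102 that is 84.9 − 79.2 = 5.7 percentage points for r = 1%, and 84.9 − 64.9 = 20.0 points for r = 3%.

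**The case against.** The strongest reply is that the test is not ambiguous. Section 3.2.1 is headed as the primary endpoint, 3.2.6 repeats it with the same safety wording, and the hypotheses attach to that version. An analyst following 3.2 has one definition to program, and the likelier defect is that 2.2 was not aligned. This stands. A reader might infer that the primary test is undefined, and the documents do not support that. What remains is that the objective in 2.2 says something else and no statement gives either version precedence.

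A second reply is that the differing group may be small. A subject belongs to it only if index-level surgery occurred, no device-related SAE was adjudicated, and the pain, function and CT criteria were still met. On the narrow reading it is smaller again. This also stands, and it is why no value of r is claimed. The group is not empty by design, however: hardware loosening and breakage are listed risks in 7.2.3 and imaging findings to be looked for in Section 6.0.

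Third, the threshold of 65 assumes 102 complete subjects. The plan expects 15% loss and imputes by LOCF and then multiple imputation, so the actual decision may not be a simple count. That is correct, and the threshold is given only for scale.

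Finally, imposing the broadest reading of 2.2 is a design choice with a power cost, not a correction the documents require. That is accepted, and the fix leaves the choice to the sponsor.

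**Conclusion.** The inconsistency is real and rests on current text alone. The endpoint tested against 55% omits a condition that the stated primary objective includes. On the plain reading of 2.2, a subject with a hardware revision or other index-level re-operation not adjudicated as a device-related SAE can be a success in the test and a failure on the objective. On the narrow reading, only device-related surgery meeting no SAE criterion differs.

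The size cannot be determined from the documents. With 102 complete subjects, one to five reclassified subjects would reverse a result of 65 to 69 successes.

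A reader might infer that the false-positive rate is inflated. That would follow only if 2.2 governs. For example, with a true 2.2 rate of exactly 55% and r of 1% or 3%, the 3.2.6 test would pass with probability 7.0% or 14.2%, that is P(X ≥ 65 | n = 102, 0.55 + r). The documents do not support that premise: the goal appears only in 3.2, attached to the 3.2 endpoint, and no derivation ties 55% or 68% to the stricter definition. If 3.2.6 governs, the exact size is 4.6% and nothing is inflated.

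**What to change.** Before the 12-month interim look used for sample size re-estimation (3.2.5):

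- Use one safety component, in the same words, in 2.2, 3.2.1 and 3.2.6.
- State which definition the 55% goal and the 68% assumption were set for.
- Prespecify a sensitivity analysis giving the success rate under the other definition. The stricter version counts any index-level removal, revision, re-operation or added fixation through 24 months as failure; the looser counts device-related SAEs only. Name added fixation explicitly, because the Section 11 re-operation definition excludes it and the revision definitions do not mention it.
- Use one meaning of device related in 8.1 and Section 11, since both versions depend on it.

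The cost is wording in a few sections and one extra analysis of adverse-event and treatment information that the protocol already captures. Aligning 2.2 to 3.2.6 costs no power, but it openly removes secondary surgery from the stated objective. Making the stricter version primary keeps the objective. If 68% was set for the looser version, power must then be restated (79.2% or 64.9% at 102, for an assumed 1 or 3 points, against 84.9%) or dealt with in the planned re-estimation.

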3.2.1 Primary Endpoint

The primary endpoint (success) is a composite endpoint of pain, function, fusion, and safety, defined as meeting each of the following criteria at the 24-month study interval:

- Pain – Improvement in low back pain score evidenced by a 20 mm reduction on a 100 mm Visual Analog Scale (VAS) when compared to baseline (Note: a lower VAS pain score indicates less pain),
- Function – Improvement in low back function evidenced by a 15 point decrease of the Oswestry Disability Index (ODI) score compared to baseline. (Note: a higher ODI score indicates a greater disability with respect to low back function),
- Fusion – Bridging bone demonstrated on CT Scan
- Safety – Freedom from investigational device-related Serious Adverse Events at the index level through the 24-month study interval.

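### Section 3.2.6 puts no failure-first rule ahead of imputation, so deaths and exits after index-level surgery can be scored as Month-24 successes

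*Combined protocol and SAP*

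**What the plan says.** Section 3.2.6 (Analysis of Primary Endpoint) handles a missing Month-24 composite in two steps. LOCF comes first, for a subject missing no more than one component who has that component at Month 12. Then "multiple imputation methods will be used to impute values for the remaining subjects with missing values for the primary endpoint at Month 24", with a model built on post-baseline primary endpoint data from earlier visits. Neither step carries an exception for death, for surgery at the treated level, or for a criterion already failed.

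Three other provisions bear on this:

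- **Denominator.** Section 3.2.3: "All analyses of effectiveness and safety will be based upon the Treated Population defined to be all treated subjects". Subjects who die or leave therefore stay in the analysis. Section 3.2.9 also keeps the data collected before a voluntary withdrawal.
- **Safety component.** Sections 3.2.1 and 3.2.6 define it as "Freedom from investigational device-related Serious Adverse Events at the index level through the 24-month study interval". Section 2.2 (Investigation Objectives) adds freedom from secondary surgical interventions at the index level. The analysis sections do not name them.
- **Test.** Section 3.2.6: "The null hypothesis will be tested using a 1-sided exact binomial test for a binomial proportion conducted at the 0.05 level of significance", against a performance goal of 55%.

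**The concern.** Success requires every criterion to be met at 24 months. A subject who has died cannot be observed to meet them. A subject who has had index-level surgery fails under Section 2.2. Yet the imputation text does not score either one as a failure.

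Pain and function both come from the Patient Survey, so a subject who dies or leaves normally lacks both at Month 24. That is two missing components, so LOCF does not apply and multiple imputation does. A subject who stays after index-level surgery but misses a single component can have the Month-12 value carried forward instead. Under 3.2.1 and 3.2.6, a death or a reoperation fails the composite only if it is adjudicated a device-related serious adverse event.

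Any such subject scored as a success moves the result toward the device. In a single-arm trial against a fixed goal, no comparator takes the same bias and offsets it.

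**Working it through.** **Inputs from the plan (3.2.3, 3.2.4, 3.2.6).** One-sided exact binomial test, alpha 0.05, goal 55%, assumed true rate 68%, power 80%, 87 evaluable, 102 enrolled to allow for 15% loss.

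**Reproducing the plan's figure.** At n = 87 the smallest passing count is 56:
- P[Bin(87, 0.55) ≥ 56] = 0.0487 (alpha).
- P[Bin(87, 0.68) ≥ 56] = 0.801 (power).

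87 is the smallest n that reaches 80% power, so the stated figure is confirmed. 87/0.85 = 102.4, which the plan gives as 102.

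**Rule with all treated subjects analysed.** At n = 102:
- P[Bin(102, 0.55) ≥ 64] = 0.0697.
- P[Bin(102, 0.55) ≥ 65] = 0.0464.

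The trial passes at 65 or more, with a base error of 4.6%. Power at 68% is 0.849.

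**Effect of imputing.** Suppose k of the 102 are truly failures but have a missing composite, and each is scored a success with chance q. The documents give neither k nor q. Hold the true overall rate at 55%, so the rate in the other subjects is p_k = 0.55 × 102/(102 − k):
- p_1 = 0.5554
- p_2 = 0.5610
- p_3 = 0.5667

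The false-pass probability is

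Σ_j C(k, j) q^j (1 − q)^(k − j) × P[Bin(102 − k, p_k) ≥ 65 − j], for j = 0 to k.

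For k = 1 the two tails are P[Bin(101, 0.5554) ≥ 65] = 0.0454 and P[Bin(101, 0.5554) ≥ 64] = 0.0684. Hence:
- q = 0.10: 0.90 × 0.0454 + 0.10 × 0.0684 = 0.048
- q = 0.25: 0.75 × 0.0454 + 0.25 × 0.0684 = 0.051
- q = p_1 = 0.5554: 0.4446 × 0.0454 + 0.5554 × 0.0684 = 0.058

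| k | counted as failures | q = 0.10 | q = 0.25 | q = p_k (about 0.56) |
|---|---|---|---|---|
| 1 | 4.5% | 4.8% | 5.1% | 5.8% |
| 2 | 4.4% | 4.9% | 5.6% | 7.2% |
| 3 | 4.3% | 5.0% | 6.2% | 9.0% |

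**Cross-check.** A simulation of 40,000 trials with 20 imputations each, imputing at the observed success rate, gave errors of 6.2, 7.6 and 9.6% when 1, 2 and 3% of subjects were such failures (median exact p-value across imputations). With these subjects scored as failures, it stayed between 4.5 and 4.8%. The median p-value was chosen for this check because the plan does not say how the exact test is combined across imputations.

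**Where q might lie.** The model uses earlier endpoint data, so a subject doing badly before leaving should get a low q. On the other hand, CT is first scheduled at 12 months (Table 1), so a subject lost before then has no earlier value of the full composite. The plan does not say whether component scores enter the model. If they do not, q falls near the overall rate. A subject doing well before an unrelated death could have a higher q still.

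**The case against.** The strongest reply is that a composite with one failed criterion is not missing. Success means meeting all criteria, so a single observed failure fixes the value, and LOCF is itself described as a way to let the value be determined. A device-related serious adverse event stays on record after withdrawal and fails a criterion that runs through Month 24. On that reading the plan already scores known failures correctly. This stands as a sensible interpretation. A reader might infer that the plan directs known failures to be imputed, but the documents do not say that. They are silent, and the rule should be written down.

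The reply does not reach the other two groups. A death not adjudicated device-related fails no criterion in 3.2.6, and neither does index-level surgery that is not a device-related serious adverse event. For the same reason they cannot be called known failures under 3.2.6. Surgery is a failure only under 2.2, and the treatment of an unrelated death is a choice of estimand that the plan has to state.

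Three other stronger readings also fail:
- That every missing endpoint is multiply imputed: LOCF comes first.
- That these subjects would mostly be imputed as successes: the model draws on earlier endpoint data, and at q = 0.10 the error barely reaches 5%.
- That the absence of a 24-month CT always means a missing fusion value: Table 1 and Section 6.0 schedule that scan only for subjects not fused at 12 months.

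**Conclusion.** The gap is real. Section 3.2.6 has no rule that takes determined failures out before imputation, and it leaves deaths and exits after index-level surgery open to being scored as successes. The direction is certain, since any q above zero raises the false-pass probability above its value when these subjects are counted as failures.

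The size is not certain. For one to three such subjects it runs from 4.8–5.0% at q = 0.10, through 5.1–6.2% at q = 0.25, to 5.8–9.0% at q of about 0.56. These figures assume a true rate of exactly 55%, all 102 subjects analysed, and the stated k and q. The upper age limit of 80 with 24 months of follow-up makes some deaths plausible but supplies no rate. The exact test has little slack to absorb the bias, because its base error of 4.6% is already close to the 5% limit.

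**What to change.** First reconcile the safety component in 3.2.1 and 3.2.6 with Section 2.2, so that one definition settles whether index-level secondary surgery is a failure. Then insert before the LOCF step in 3.2.6:

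> A subject who has failed the safety component at any time through Month 24, or has an observed Month-24 failure on pain, function or fusion, is a failure and is not imputed. Subjects who die before Month 24 are counted as failures in the primary analysis, with a sensitivity analysis that imputes deaths unrelated to the device. LOCF and multiple imputation apply only to subjects whose composite is undetermined.

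The sentence is limited to observed Month-24 failures on purpose. A not-fused reading at 12 months alone is not a determined failure, because the protocol schedules a second CT for that subject. It also refers to the safety component as reconciled, and does not list removals or revisions, so that it does not create a third safety definition.

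The cost is a short text change and possibly a slightly less favourable success rate. Sample size need not change: with these subjects counted as failures, the error is at most 4.6%, and power at a true overall rate of 68% stays about 0.85 with all 102 subjects.
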